12.8 Rules for Excluding Subjects from Analysis

All dosed subjects will be included in the analyses unless otherwise specified. The sponsor will make any decisions regarding whether any subjects or any individual values belonging to a subject will be excluded from the evaluations when the protocol violation is considered to have a negative impact on the scientific aspects and interpretation of the study results. If the subject has received any IMP, all available safety data will be used. The reason(s) for any exclusion will be described in the report.

12.9 Procedures for Reporting Deviations from Original Statistical Plan

Any deviations from the statistical analysis outlined in this protocol will be described, and reasons for the deviations listed, in the final Clinical Study Report.

13 SPECIAL REQUIREMENTS AND PROCEDURES

13.1 Regulatory and Ethical Considerations

This study will be conducted in accordance with the protocol and with the following:

- Consensus ethical principles derived from international guidelines including the Declaration of Helsinki and Council for International Organizations of Medical Sciences (CIOMS) International Ethical Guidelines
- Applicable ICH GCP Guidelines
- Applicable laws and regulations

Before starting this study, the protocol (authorized by the sponsor), Informed Consent Form, Investigator Brochure, and other relevant documents (e.g., advertisements) must be submitted to an IEC/IRB for evaluation and reviewed and approved by the IEC/IRB. The protocol will also be submitted to regulatory bodies/local health authorities in accordance with local regulations as required. The study will not start before the IEC/IRB gives written approval or a favorable opinion in accordance with ICH E6-GCP and all applicable regulatory bodies/local health authorities give approval or a favorable opinion as required.

No changes from the final approved (authorized) protocol will be initiated without the IEC's/IRB's prior written approval or favorable opinion of a written amendment, except when necessary to eliminate immediate hazards to the subjects or when the change involves only logistics or administration. The sponsor will authorize and the principal investigator(s) will sign the protocol amendment prior to submission to the IEC/IRB. Protocol amendments should be submitted to the IEC/IRB without delay. Any significant deviation from the protocol when no approved amendment exists will be regarded as a protocol violation, and will be addressed as such during the reporting of the study.

The investigator will be responsible for the following:

- Providing written summaries of the status of the study to the IEC/IRB annually or more frequently in accordance with the requirements, policies, and procedures established by the IEC/IRB
- Notifying the IEC/IRB of SAEs or other significant safety findings as required by IEC/IRB procedures
- Providing oversight of the conduct of the study at the site and adherence to requirements of 21 CFR, ICH guidelines, the IEC/IRB, European regulation 536/2014 for clinical studies (if applicable), and all other applicable local regulations.

13.2 Investigator's Responsibilities

13.2.1 Overall Responsibilities

The investigator(s) is/are responsible for conducting the study in full accordance with the Protocol and the Declaration of Helsinki, the *Good Clinical Practice: Consolidated Guideline*, approved by the ICH, and any applicable national and local laws and regulations. Information regarding any investigational centers participating in this study that cannot comply with these standards will be documented.

13.2.2 Parental Permission/Subject Informed Assent

Written and oral information about the study in an understandable language will be given to the subject and subject's parent/legal guardian. Each subject's willingness to participate in the study will be documented in a signed and dated informed assent form and parental informed permission form before any procedures or assessments are performed and after the aims, methods, anticipated benefits, potential hazards, and insurance arrangements in force are explained. Age-appropriate pediatric assent will be obtained where required.

It will also be explained to the subject and the subject's parent/ legal guardian that they are free to refuse to participate in the study and free to withdraw from the study at any time without prejudice to future treatment.

The informed consent/assent process will be documented in the subject's medical record and the investigator will sign, date and time the informed consent form after the subject's parent/legal guardian have signed, dated and recorded the time.

The investigator(s) will keep the original consent forms and copies will be given to the subjects or the subject's parent/legal guardian.

13.2.3 Direct Access to Source Data/Documents

Source documents provide evidence for the existence of the subject and substantiate the integrity of the data collected. Source documents are filed at the investigator's site.

Data reported on the CRF or entered in the electronic CRF that are transcribed from source documents must be consistent with the source documents or the discrepancies must be explained. The investigator may need to request previous medical records or transfer records, depending on the study. Also, current medical records must be available.

The monitor(s), auditor(s), authorized personnel of the sponsor, health authority inspector(s) or their agents, and authorized members of IECs/IRBs will be given direct access to source data and documentation (e.g., medical charts/records, laboratory results, printouts, videotapes, etc.) for source data verification, provided that subject confidentiality is maintained in accordance with local requirements.

13.2.4 Confidentiality Regarding Study Subjects

The investigator(s) must assure that the privacy of the subjects, including their personal identity and all other personal medical information, will be maintained at all times. In CRFs and other documents or image material (including materials from all examinations, e.g., ultrasound examinations) submitted to the sponsor, subjects will not be identified by their names, but by an identification code (e.g., initials and study subject number).

Personal medical information may be scrutinized for the purpose of verifying data recorded in the CRF. This may be done by the monitor(s), properly authorized persons on behalf of the sponsor, the quality assurance unit, or regulatory authorities. Personal medical information will always be treated as confidential.

13.2.5 Data Protection

Subjects will be assigned a unique identifier by the sponsor. Any subject records or datasets that are transferred to the sponsor will contain the identifier only; subject names or any information which would make the subject identifiable will not be transferred.

The subject and subject's parent/legal guardian must be informed that his/her personal study-related data will be used by the sponsor in accordance with local data protection law. The level of disclosure must also be explained to the subject and subject's parent/legal guardian who will be required to give consent for their data to be used as described in the informed consent.

The subject and subject's parent/legal guardian must be informed that his/her medical records may be examined by Clinical Quality Assurance auditors or other authorized personnel appointed by the sponsor, by appropriate IEC/IRB members, and by inspectors from regulatory authorities.

13.3 Protocol Deviations

Any deviation from the protocol when no approved amendment exists must be documented as a protocol deviation and reported according to local requirements. If appropriate, corrective and preventative action must be implemented to avoid repetition. Protocol deviations and any potential impact on the study results will be discussed during the reporting of the study.

Waivers or protocol exceptions will not be granted prospectively by the sponsor under any circumstances.

13.4 Study Monitoring

Study monitoring will be performed in accordance with ICH E6-GCP, the sponsor SOPs, the protocol, and applicable local regulations.

13.5 Audit and Inspection

According to ICH E6-GCP, the sponsor or regulatory authorities may audit the investigational site. The sponsor's Quality Assurance Unit, independent of the Clinical Research and Development Department, is responsible for auditing the study.

The investigator(s) must accept that regulatory authorities may conduct an inspection to verify compliance of the study with GCP.

13.6 Financial Disclosure

According to 21 CFR, Part 54, the sponsor is required to completely and accurately disclose or certify information concerning the financial interests of a clinical investigator (or investigating institution) who is not a full-time or part-time employee to the FDA. Therefore, the investigator(s) (or investigating institution) must either provide the sponsor with sufficient, accurate financial certification that none of the following financial arrangements (further defined in 21CFR Part 54.2) exist with the sponsor or fully disclose the nature of the arrangement. This financial disclosure also applies to any financial arrangements that exist between the sponsor and the investigator's spouse(s) or dependent children:

- Compensation for participation in the study is affected by the outcome of the study.
- Significant equity (greater than \$50,000) interest in the sponsor's company.
- Proprietary interest in the tested product.
- Significant payments of other sorts, exceeding a monetary value of \$25,000.

13.7 Insurance

This study is covered under the sponsor's Liability Insurance Policy (under General Electric Insurance Company and/or a company designated by the study sponsor). A Certificate of Insurance and/or an information leaflet containing essential information about the insurance coverage can be provided upon request.

13.8 Publication Policy

The investigator and/or Institution shall have the right to publish the results of their work conducted under this protocol, subject to providing the sponsor with the opportunity to review the contents of any proposed abstract or publication concerning the work, including any results of the study, in advance of publication and if necessary to delay publication for a limited time not to exceed 60 days in order to protect the confidentiality or proprietary nature of any information contained therein. The sponsor will make every reasonable effort to consider and release each proposed publication within 30 days, or proposed abstract within 15 days, of submission.

15 APPENDICES

15.1 Information on Investigational and Registered Products

The currently approved OPTISON package insert or Summary of Product Characteristics will be provided to all investigators as a separate document. The package insert/Summary of Product Characteristics provides information on the efficacy and safety of the OPTISON, and is used for assessing expectedness of Serious Adverse Drug Reactions, in order to determine regulatory reportability. An unexpected Adverse Drug Reaction is a reaction, for which the nature, seriousness, severity or outcome is not consistent with the applicable product information presented in the package insert/Summary of Product Characteristics.

15.2 Equipment Parameters

Please refer to the Imaging Manual.

15.3 Pediatric Normal Ranges

Table 5 Pediatric Vital Signs Normal Ranges

Age Group	Respiratory Rate	Heart Rate	Systolic Blood Pressure	Weight in kilos	Weight in pounds
Newborn	30 – 50	120 – 160	50 – 70	2 – 3	4.5 – 7
Infant (1-12 months)	20 – 30	80 – 140	70 – 100	4 – 10	9 – 22
Infant (1-12 months)	20 – 30	80 – 140	70 – 100	4 – 10	9 – 22
Preschooler (3-5 yrs.)	20 – 30	80 – 120	80 – 110	14 – 18	31 – 40
School Age (6-12 yrs.)	20 – 30	70 – 110	80 – 120	20 – 42	41 – 92

REF: Source: <http://www.rnceuus.com/psvt/psvtvs.html>

Table 6 Pediatric ECG Normal Ranges

ECG Variable	Mean (sd)	1 st %ile	5 th %ile	Median	95 th %ile	99 th %ile
Heart Rate (bpm)	83.0 (12.1)	59.0	65.0	82.0	104	114.0
RR Interval (ms)	738.5 (107.8)	526.3	576.9	731.7	923.1	1040.0
PR Interval (ms)	132.8 (17.3)	100.0	108.0	130.0	162.0	180.0
QRS Interval (ms)	80.0 (9.0)	64.0	70.0	80.0	96.0	102.0
QT Interval (ms)	354.7 (24.3)	300.0	318.0	352.0	396.0	416.0
QTc Bazett (ms)	414.0 (19.6)	367.0	383.0	414.0	443.0	460.0
QTc Data-derived (ms)	399 (17.3)	357.4	372.0	398.7	424.1	439.6
QTc Fridericia (ms)	393.2 (17.1)	353.3	366.3	392.9	419.0	433.0

Note: Pre-pubertal group (N = 1537) defined as females whose age was \leq 8 years (n = 224) and males whose age was \leq 9 years (n = 1313). Abbreviations: RR, Duration of ventricular cardiac cycle (an indication of ventricular rate); PR, Time from the onset of atrial depolarization (P wave) to onset of ventricular depolarization (QRS complex); QTcb, Bazett's method for QT interval correction; QTcd, Data-derived corrected method for QT interval correction; QTcf, Fridericia's method for QT interval correction.

Table 7 Mean and Percentiles of ECG Cardiac Measures Among Pubertal Children

ECG Variable	Mean (sd)	1 st %ile	5 th %ile	Median	95 th %ile	99 th %ile
Heart Rate (bpm)	77.4 (11.8)	54.0	60.0	76.0	98.0	109.0
RR Interval	792.9 (121.1)	555.6	612.2	780.0	1000.0	1132.0
PR Interval (ms)	136.8 (18.5)	100.0	112.0	136.0	170.0	109.0
QRS Interval (ms)	83.0 (9.1)	68.0	70.0	80.0	96.0	106.0
QT Interval (ms)	368.8 (27.0)	310.0	330.0	368.0	412.0	440.0
QTc Bazett (ms)	415.6 (21.3)	362.0	381.0	416.0	448.0	468.0
QTc Data-derived (ms)	403.9 (19.1)	357.0	373.3	404.0	433.1	450.1
QTc Fridericia (ms)	399.4 (19.0)	354.5	369.4	399.6	429.0	443.9

Note: Pubertal group (N = 3656) defined as females whose age was > 8 and ≤ 13 years (n = 881) and males whose age was > 9 and ≤ 14 years (n = 2775).

Abbreviations: RR, Duration of ventricular cardiac cycle (an indication of ventricular rate); PR, Time from the onset of atrial depolarization (P wave) to onset of ventricular depolarization (QRS complex); QTc_b, Bazett's method for QT interval correction; QTc_d, Data-derived corrected method for QT interval correction; QTc_f, Fridericia's method for QT interval correction.

Source: Child and Adolescent Psychiatry and Mental Health 2007;1:11

16 CLINICAL PROTOCOL AMENDMENT SUMMARIES

16.1 Amendment A01

16.1.1 Reasons for Amendment

- The requirement for a minimum of 10 subjects to be enrolled in each body weight group is removed.
- The requirement to record the vial code in the CRF is removed.

16.1.2 Description of Changes

Where appropriate, the changes documented below are also made in the synopsis.

Section 6.1, Overall Study Design and Plan, Third Paragraph

Previously read:

Each patient will undergo an echocardiographic procedure first without contrast administration then following intravenous bolus injection of OPTISON at various doses. The dose of OPTISON for each subject will be determined according to pediatric body weight group and 2 different dose levels will be tested in each subject. A minimum of 10 subjects will be enrolled in each body weight group. The details on OPTISON administration are presented in Section 8.1 of this protocol.

Now reads:

Each patient will undergo an echocardiographic procedure first without contrast administration then following intravenous bolus injection of OPTISON at various doses. The dose of OPTISON for each subject will be determined according to pediatric body weight group and 2 different dose levels will be tested in each subject. The details on OPTISON administration are presented in Section 8.1 of this protocol.

Section 8.6, Treatment Compliance

Previously read:

Subjects will receive OPTISON administration under direct supervision of study personnel. Each administration volume will be checked and the vial code and volume per administration will be recorded in each subject's CRF.

Now reads:

Subjects will receive OPTISON administration under direct supervision of study personnel. Each administration volume will be checked and the volume per administration will be recorded in each subject's CRF.

SIGNATURE PAGE

Date / Name

Signed By: [REDACTED]

Date of signature: 04-Oct-2022 08:33:15 GMT+0000

Signed By: [REDACTED]

Date of signature: 04-Oct-2022 08:53:37 GMT+0000

Signed By: [REDACTED]

Date of signature: 04-Oct-2022 12:59:26 GMT+0000

Justification / Role

Justification: Approved

Role: [REDACTED]

Justification: Approved

Role: [REDACTED]

Justification: Approved

Role: [REDACTED]

Table 5	Mean and Percentiles of ECG Cardiac Measures Among Pre-pubertal Children ..	23
Table 6	Mean and Percentiles of ECG Cardiac Measures Among Pubertal Children	24
Table 7	Mean and Percentiles of ECG Cardiac Measures Among Post-pubertal Children	24

List of Figures

Figure 1	Study Diagram	8
-----------------	----------------------------	---

Abbreviations

AE	Adverse event
ATC	Anatomical-Therapeutic-Chemical
BIE	Blinded image evaluation
CE-ECHO	Contrast-enhanced echocardiography
CHMP	Committee for Medicinal Products for Human Use
EBD	Endocardial border delineation
ECG	Electrocardiogram
eCRF	Electronic Case Report Form
ICH	International Council for Harmonisation
IMP	Investigational medicinal product
ITT	Intent-to-treat
LV	Left ventricular
LV EBD	Left ventricular endocardial border delineation
LVEF	Left ventricular ejection fraction
LVO	Left ventricular opacification
MedDRA	Medical Dictionary for Regulatory Activities
SAE	Serious adverse event
SAP	Statistical Analysis Plan
SOC	System organ class
TEAE	Treatment-emergent adverse event
WHO-DD	World Health Organization Drug-Dictionary

1 INTRODUCTION

The statistical analysis plan (SAP) defines the methods and analyses that GE HealthCare plans to use to analyze the data from Protocol GE-191-008. This SAP is based on the final study protocol (Amendment A01 Version 2.0) dated 04 October, 2022. This SAP complies with guidance promulgated by the International Conference on Harmonization (ICH) and the US Food and Drug Administration (FDA). If the protocol is subsequently amended, this SAP may be amended as well. Should the SAP and the protocol be inconsistent with respect to the planned analyses, the language of the SAP prevails.

2 STUDY OBJECTIVES, DESIGN AND PROCEDURES

2.1 Objectives

The primary and secondary objectives of the study are as follows:

Primary:

- To determine a suitable dosage of OPTISON for contrast-enhanced echocardiography (CE-ECHO) in pediatric patients.

Secondary:

- To assess the safety profile of intravenous administrations of OPTISON in the pediatric population.
- To compare diagnostic confidence of left ventricular endocardial border delineation (LV EBD) and wall motion between non-contrast and OPTISON-enhanced echocardiography.
- To compare the diagnostic confidence in the evaluation of left ventricular ejection fraction (LVEF) between non-contrast and OPTISON-enhanced echocardiography.

2.2 Study Design

This is a Phase 4, open-label, non-randomized, multi-center, multi-dose study in North America and Europe. The study is designed to evaluate overall efficacy and safety of intravenous administration of OPTISON at various doses in pediatric patients undergoing transthoracic echocardiography.

Approximately 50 pediatric patients between ≥ 9 and <18 years of age weighing ≥ 20 kg who are clinically indicated for a transthoracic echocardiogram and are likely to have a limited transthoracic echocardiographic window based on body habitus and/or previous cardiac operation or have a previous suboptimal non-contrast echo cardiogram will be enrolled into the study. Per FDA Advice/information request dated 2023, February 16th, a reduction of the sample size to 30 evaluable subjects was agreed.

OPTISON will be administered according to pediatric body weight (≥ 20 to ≤ 28 kg, >28 to ≤ 40 kg, and >40 kg). Each patient will receive administrations of 2 different dose levels. Up to 3 injections per dose level are allowed to be administered if significant technical issue(s) have occurred e.g., patient related needs, scanner malfunction, or drug injection error, with the total injected dose not to exceed the value defined in Table 1. Injections should be at least 10 minutes apart between the 2 dose levels to allow for clearance of the previous dose.

Table 1 OPTISON Dosing Table

Body weight (kg)	Dose/injection (mL) Dose level 1	Dose/injection (mL) Dose level 2	Total dose (mL) not to exceed (3 injections/dose level)
≥ 20 to ≤ 28	0.1	0.2	1.0
>28 to ≤ 40	0.2	0.3	1.5
>40	0.2	0.4	1.8

[figure not shown]
For echocardiographic imaging, standard apical 4-chamber and 2-chamber views will be obtained at baseline using tissue harmonic imaging, thereafter with contrast using a contrast-imaging mode. Additional views may be obtained at the clinician's discretion. All image views will be obtained prior to and after contrast administration until 10 minutes post injection. All images will be recorded on disk and sent to sponsor's image core lab for preparation of blinded image evaluation (BIE).

Efficacy of echocardiographic images will be evaluated by independent blinded readers based on characteristics of left ventricular opacification (LVO), diagnostic confidence of LV EBD and wall motion, and diagnostic confidence of LVEF. Echocardiographic Analyses as per independent review charter includes:

1. Evaluation of Left ventricular (LV) Endocardial Border Delineation (EBD)
2. Evaluation of diagnostic confidence for the assessment of LV EBD and wall motion
3. Evaluation of Left Ventricular Opacification (LVO)
4. Evaluation of Image Quality and Diagnostic Usefulness
5. Evaluation of Left Ventricular Function
6. Evaluation of diagnostic confidence for the assessment of LVEF
7. Evaluation of Duration of Contrast Enhancement.

Clinical safety data will be collected throughout the study, beginning from dosing through 72 hours post OPTISON administration to determine the safety profile of intravenous administration of OPTISON at various doses in pediatric population.

Figure 1 Study Diagram

All efficacy and safety measurements obtained during the course of the study are summarized in the Study Schedule of Events ([Table 2](#)).

Table 2 Study Schedule of Events

Variables	Pre-procedure		Dosing/ Imaging (0)	Post-last OPTISON Administration				
	Screening (≤2 weeks)	Baseline (from -1 ± 1 h)		10 min (±5 min)	30 min (±5 min)	1 h (±5 min)	24 h (±4 h)	72 h (±8 h)
Informed Consent	X							
Entry Criteria	< ----- >							
Demographic Information	X							
Medical/Surgical History	X							
Pregnancy test ^a	X	X						
Physical Examination		X				X		
Vital Signs		X		X		X		
SaO ₂ by Pulse Oximetry		X	X	X		X		
12-Lead ECG Recording		X		X	X			
Prior and concomitant Medications ^b		< ----- >						
Continuous ECG Monitoring ^c			< ----- >					
OPTISON Administration			X					
Image Acquisition		X	X					
Phone Calls							X	X
AEs and SAEs Monitoring	X	<----->						

AE = Adverse event; ECG = Electrocardiogram; SAE = Serious adverse event; SaO₂ = Oxygen saturation

a Urine β-hCG pregnancy test at screening and at pre-dose; post-menarchal females only.

b Any prior or concomitant medication taken by the subject within 24 hours before OPTISON injection and up to the end of the 72-hour follow-up period.

c Continuous ECG monitoring is from time of first OPTISON injection until 30 minutes after the last OPTISON injection

2.3 Sample Size

Although this is a dose-finding study and no hypotheses are being tested, it was thought useful to estimate sample size based on one of the study endpoints as a guide. Since there is no historical literature about LV EBD results for OPTISON, the power estimation is based on the endpoint of contrast enhancement duration.

A paired t-test was used for this power analysis with a one-sided significance level of 0.025. The null hypothesis is that the mean value of (contrast enhancement duration for

the high dose – contrast enhancement duration for the low dose within the same patient) ≤ 0 minutes, and the alternative hypothesis is that the mean value of (contrast enhancement duration for the high dose – contrast enhancement duration for the low dose within the same patient) > 0 minutes. Based on the results from [Cohen et al. 1998], we assume that the estimated mean value of (contrast enhancement duration for the high dose – contrast enhancement duration for the low dose within the same patient) equals 0.7 minutes, with a standard deviation of 1.5 minutes. [Table 3](#) displays the power calculation for the hypothesis testing with different sample sizes.

Table 3 Power Calculation

Total sample size	Power
30	70%
40	82%
50	90%
60	94%
70	97%
80	98%

Therefore, the sample size for this clinical investigation was approximately 50 subjects, which would provide at least 90% power to detect an efficacy difference of 0.7 minutes between the high and low doses, with the greater duration for the high dose. In addition, a sample size of 50 was considered to be adequate to address the other efficacy endpoints (LV EBD, LVO characteristics, wall motion assessment, and diagnostic confidence for the evaluation of LVEF) and OPTISON’s safety profile following intravenous administration in pediatric subjects. The data will support dosing information in children. Per FDA Advice/information request dated 2023, February 16th, a reduction of the sample size to 30 evaluable subjects was agreed.

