4 ANALYSIS POPULATIONS

4.1 Definition for Analysis Populations

Enrolled subjects are subjects who signed the informed consent.

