4.1.2 Full Analysis Set (FAS) Population

The FAS population will include all subjects enrolled in the study who have available non-contrast harmonic images and OPTISON-enhanced echocardiographic images, irrespective of the quality of CE-ECHO.

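### Does the SAP's cut to 30 evaluable subjects leave its sample-size statement wrong, given that the power and adequacy conclusions are still written for about 50?

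*SAP*

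**What the plan says.** SAP 2.3 presents the power calculation as a guide: "it was thought useful to estimate sample size based on one of the study endpoints as a guide". The endpoint is contrast enhancement duration, which is secondary. The test is a within-patient comparison of high against low dose. Table 3 runs from 30 subjects (70%) to 80 (98%).

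The conclusion is for 50: "Therefore, the sample size for this clinical investigation was approximately 50 subjects, which would provide at least 90% power to detect an efficacy difference". The next sentence adds that "a sample size of 50 was considered to be adequate to address the other efficacy endpoints", and extends this to safety. The section ends by recording, after an FDA communication of February 2023, that "a reduction of the sample size to 30 evaluable subjects was agreed".

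SAP 2.2 describes the population in a sentence that opens "Approximately 50 pediatric patients between" and ends "have a previous suboptimal non-contrast echo cardiogram will be enrolled into the study". The sentence on 30 evaluable subjects follows at once.

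SAP section 4 defines four groups. "Enrolled subjects are subjects who signed the informed consent". The Safety population requires at least one administration. For efficacy, "The FAS population will include all subjects enrolled in the study who have available non-contrast harmonic images and OPTISON-enhanced echocardiographic images", whatever the quality of the contrast study. The PP set is the FAS without important deviations that affect the primary endpoint. None of these is called evaluable.

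**The concern.** Three things look wrong together. First, the current target is 30, but the only conclusions about power and adequacy are for 50, so a quick reader could carry 90% power over to a study that has about 70%. Second, SAP 2.2 still says in the future tense that about 50 will be enrolled, and the SAP gives no other enrolment number. Third, *evaluable* is undefined: enrolled means consent signed, the FAS needs images, and the FAS wording does not expressly ask for images at both dose levels, which a paired comparison uses.

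If the power figure supported a planned test, this would matter: the stated chance of success would be about 20 points too high, and it would be unclear which subjects count towards the target.

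**Working it through.** **Inputs (SAP 2.3):** paired t-test, one-sided alpha 0.025, mean within-patient difference 0.7 min, SD of the difference 1.5 min.

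**Step 1. Reproduce Table 3.** Power = P(T > t(0.975, n−1)), where T is noncentral t with n−1 degrees of freedom and noncentrality (0.7/1.5)·√n = 0.4667·√n.

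| n | noncentrality | computed power | Table 3 |
|---|---|---|---|
| 30 | 2.556 | 69.5% | 70% |
| 40 | 2.951 | 82.1% | 82% |
| 50 | 3.300 | 89.9% | 90% |
| 60 | 3.615 | 94.47% | 94% |
| 70 | 3.904 | 97.1% | 97% |
| 80 | 4.174 | 98.47% | 98% |

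Every row agrees to rounding. At 50 the unrounded value is just under 90% (51 subjects reach it), which is not a material error. The test is within patient, so a total sample size of 30 in the table means 30 pairs. The correct guide power for the reduced size is already printed.

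**Step 2. What 30 costs on the guide endpoint.** The expected 95% CI half-width is t(0.975, n−1)·1.5/√n:

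- n = 30: 2.045 × 1.5/5.477 = 0.56 min
- n = 50: 2.010 × 1.5/7.071 = 0.43 min

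With 30 pairs, the true difference that gives 90% power is about 0.92 min, against 0.70 min with 50.

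**Step 3. What 30 costs on safety.** With no events seen, the one-sided 95% upper bound on an event rate is 1 − 0.05^(1/n): 9.5% at 30 and 5.8% at 50. This is a consequence of the agreed size. Rewording SAP 2.3 would not alter it.

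**Step 4. Does any planned analysis use the affected text?**

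- SAP 6.4.1 says no hypotheses are tested.
- The paired t-tests in SAP 6.4.2 compare non-contrast with each dose, on segments visualized and on total EBD score. None compares high with low dose.
- SAP 6.4.3 summarizes duration descriptively by dose level.
- SAP 2.4 plans no interim analysis, so no stopping boundary or information fraction uses the target.
- Who is analysed is set by the Safety, FAS and PP definitions. Whether a subject counts towards the 30 does not decide whether that subject is analysed.

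**Step 5. How far could the missing definition move the pair count?** Each patient is to receive both dose levels (SAP 2.2). Protocol 7.4.1 replaces a subject withdrawn before the contrast study is complete. Under SAP 6.4.4 an uninterpretable image counts as zero duration, so in the FAS that subject stays in as a pair. Only images that are absent altogether at one dose level remove a pair.

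The enrolment needed for 30 evaluable depends on a non-evaluable rate that the documents do not give. For assumed rates of 0%, 5%, 10% and 20%, it is 30, 32, 34 and 38.

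**The case for a change.** The best case for a change is that the SAP prevails over the protocol on planned analyses, so it should state its own target plainly. The 70% row helps only if the 30 evaluable subjects are 30 complete pairs, which is not stated. The adequacy sentence for the other endpoints and safety stays tied to 50, and SAP 6.4.2 reports confidence intervals, so readers have an interest in precision. Leaving *evaluable* open also leaves some discretion over when enrolment is complete. Wording would settle all of this cheaply.

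Part of this stands. The update is incomplete: SAP 2.3 was moved to the past tense and SAP 2.2 was not, and no set is named for the 30.

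The rest carries less weight. Precision on the guide endpoint follows from the SD and sample size that SAP 2.3 gives. The FAS is the natural reading of *evaluable*, since it requires both kinds of image and ignores quality. A stricter reading based on usable images would make image quality, itself an efficacy outcome, a condition for being counted. The discretion over enrolment affects a few subjects, while the efficacy scores come from readers who have no dosing information. The advice behind 30 may also fix the meaning, and it is not among these documents.

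**Conclusion.** No change to the plan follows. This is an incomplete edit after an agreed reduction, and the reduction is disclosed in both places where the older number appears. The SAP does not claim 90% power at 30: its table gives 70%, and recomputation gives 69.5%.

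The loss from 50 to 30 is real on the guide endpoint, about 20 points of power and 0.13 min of CI half-width (0.56 − 0.43). It comes from the agreed size, and no planned test of high against low dose depends on it. An analyst who follows the SAP as written would use the same populations, produce the same tables and reach the same conclusions as with tidier wording.

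This rests on the SAP's assumed difference and SD, on reading the 70% row as 30 within-patient pairs, and on taking the agreement to 30 as stated. Whether 30 is enough for the other endpoints and safety cannot be judged from these documents. The protocol predates the reduction and is not in error.
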